#### 8.5 Study Termination

NCI, DCP as the study sponsor has the right to discontinue the study at any time.

# 9. CORRELATIVE/SPECIAL STUDIES

# 9.1 Rationale for Methodology Selection

HR-HPV DNA testing and genotyping: The genomic DNA will be isolated using a QIAampMinElute Media Kit (QiagenInc, Valencia, CA). The purified genomic DNA will be amplified (PCR Cycler, AB 2720, Applied Biosystems, Grand Island, NY) and genotyped for HPV 6, 11, 16, 18, 26, 31, 33, 35, 39, 40, 42, 45, 51, 52, 53, 54, 55, 56, 58, 59, 61, 62, 64, 66, 67, 68, 69, 70, 71, 72, 73, 81, 82, 83, 84, IS39, and CP6108 using a Roche Linear Array (RLA) assay (Roche, Pleasanton, CA). This is a quantitative test that detects 37 high-risk and low-risk HPV genotypes.

Cytokine testing by Luminex. Cytokines (IFN-alpha2, IFN-gamma, IL-1alpha, IL-1beta, IL-6, IL-8, IL-10, IL-12 [p70 heterodimer], MIP-1alpha, and TNF) in cervicovaginal lavage will be measured by Luminex technology using Milliplex Human Cytokine Magnetic-bead Kits (Millipore Corporation, Billerica MA). Luminex assays will allow us to simultaneously detect and quantify multiple cytokines of interest. They require small sample volumes, are cost-effective, and allow researchers to collect more data in less time than other assays.

TLR and T-regulatory expression: RNA will be extracted using TRI Reagent (Molecular Research Center, Cincinnati, OH). DNase treatment (TURBO DNA-free, Ambion), reverse transcription (OmniScript RT, Qiagen, Germantown, Maryland), and quantitative PCR on TLR and Foxp3 (T-regulatory cells) mRNA expression will be performed as previously described. Using real time RT-PCR is a feasible option since the samples can be stored and processed in batches. Other options such as flow cytometry are not feasible because of the small amount of sample from the cervix and the feasibility of collecting samples.

# 9.2 Comparable Methods

Each of the proposed methods for the correlative studies has been used in previous research. We will be able to compare data generated from this study with prior research.

# 10. SPECIMEN MANAGEMENT

# 10.1 Laboratories

Clinical laboratory tests and histopathology will be performed at the UNC Clinical and Pathology Labs.

Oncogenic HPV testing and genotyping, TLR, T-regulatory, and cytokine assays will be performed in the laboratory of [name] at UCLA.

# **10.2** Collection and Handling Procedures

# **10.2.1** Clinical laboratory tests

CBC with diff: One 3 ml EDTA vacutainer tube to be collected at Screening, Week 8 and End of Study Visits. Blood tubes will be prepped, labeled, and packaged according to the recommendations from the diagnostic laboratory.

CMP: One 7 ml SST or tiger top Vacutainer tubes at Screening, Week 8 and End of Study Visits. Blood tubes will be prepped, labeled, and packaged according to the recommendations from the diagnostic laboratory.

HIV: A minimum of 5 mL of blood will be collected at Screening in a blood/separator tube/gold top. Blood tubes will be prepped, labeled, and packaged according to the recommendations from the diagnostic laboratory.

Urinalysis: A minimum of 4 mL of urine will be collected for point of care testing by the research team.

Urine Chlamydia, and Gonorrhea: No more than 15 mL of urine will be obtained at Screening from the initial stream of urine. Sample will be prepped, labeled, and packaged according to the recommendations from the diagnostic laboratory.

Urine pregnancy: A minimum of 4 mL of urine will be collected for point of care testing by the research team.

# 10.2.2 Specimens for research endpoints

The following cervical specimens will be collected in the sequence listed below.

Cervic ovaginal lavage (CVL) will be collected at Baseline, Week 8 (only for participants who choose to continue participation for an additional 8 weeks), and End of Study Visits. A continuous stream of 10 ml of normal saline will be aimed directly at and into the cervical opening to bathe the endocervix and ectocervix. The fluid will pool in the posterior fornix and then be aspirated. Repeat this procedure three times with the same fluid. The aspirate will be aliquoted into 5 x 2 ml sterile cryovials (~1.5 ml volume each) and labeled with study ID, subject ID, and visit type/date. The samples will be stored at -70 °C or below for cytokines and HPV testing.

Swab of the cervix will be collected at Baseline, Week 8 (for participants who choose to continue participation for an additional 8 weeks) and End of Study Visits. A Dacron swab will be inserted to swab the endo and exocervix. The swab will then be placed into sterile tube spiked with 2 ml normal saline. Rotate the swab against the side of the tube to remove as much fluid as possible. Vortex the tube, if possible. The fluid will be placed in a 2 ml cryovial and labeled with study ID, subject ID, and visit type/date. The samples will be stored at -70°C or below for future microbiome and metabolome analysis.

Swab of the vagina will be collected at Baseline, Week 8 (for participants who choose to continue participation for an additional 8 weeks) and End of Study Visits. A Dacron swab will be inserted to swab the walls of vagina. The swab will then be placed into sterile tube spiked with 2 ml normal saline. Rotate the swab against the side of the tube to remove as much fluid as possible. Vortex the tube, if possible. The fluid will be placed in a 2 ml cryovial and labeled with study ID, subject ID, and visit type/date. The samples will be stored at -70°C or below for future microbiome analysis.

Cervical brushing will be collected at Baseline, Week 8 (for participants who choose to continue participation for an additional 8 weeks) and End of Study Visits. A cervical cytobrush will be placed into the endocervical os and rotated gently 2 times. The cytobrush will be placed into a 5 ml cryotube prespiked with RNA later. The end of the cytobrush will be snapped off so that the brush portion can fit into the cryotube. The tube will be labelled with study ID, subject ID, and visit type/date. The samples will be stored at -70°C or below for mRNA analysis.

Cervical cells for Pap smear and HR-HPV will be obtained at End of Study Visit using ThinPrep collection devices and cytology medium. The specimen will be prepped, labeled, and packaged according to the recommendations from the UNC pathology laboratory. The sample will be submitted to UNC pathology for cytology analysis and HR-HPV testing. The remaining sample will be stored for any potential future study.

Cervical biopsies will be collected at the End of Study Visit or at a subsequent clinical visit. The specimen will be prepped, labeled, and packaged according to the recommendations from the UNC pathology laboratory. The sample will be submitted to UNC pathology for histopathology and p16 staining.

Version 3, Amendment 11, 4/9/2020 One 7 ml SST or tiger top Vacutainer tubes at Baseline, Week 8 (for participants who choose to continue participation for an additional 8 weeks) and End of study Visits. The SST tube will be held at room temperature for 30 min and then centrifuged. Serum will be aliquoted evenly into 5 x 2 ml cryovials and stored at -70°C or below. The cryovials will be labeled with study ID, subject ID, and visit date.

UAZ2016-08-02

Urine will be collected at Baseline, Week 8 (for participants who choose to continue participation for an additional 8 weeks) and End of study Visits and aliquoted  $5 \times 2$  ml cryovials (~1.5 ml volume each) and stored at -70°C or below. The cryovials will be labeled with study ID, subject ID, and visit type/date.

# **10.3** Shipping Instructions

All samples will be shipped in compliance with the International Air Transport Association (IATA) Dangerous Goods Regulations. Current shipper and institutional procedures must be followed. Biologic specimens (Category B, UN3373) will be in leak-proof primary and secondary receptacles with puncture resistant packaging and absorbent material.

Shipments are to be preceded with phone contact to the receiving lab to assure the shipment will be met and stored promptly.

Cervical specimens for cytokines, HPV testing, and mRNA analysis will be shipped overnight in batches on dry ice to the laboratory of [name] at UCLA.

[name] [name] [contact] [contact] [contact]

# 10.4 Tissue Banking

Biologic specimens collected during the conduct of each clinical trial that are not used during the course of the study will be considered deliverables under the contract and thus the property of the NCI. At study completion, NCI reserves the option to either retain or relinquish ownership of the unused biologic specimens. If NCI retains ownership of specimens, the Contractor shall collect, verify and transfer the requested biologic specimens from the site to a NCI-specified repository or laboratory at NCI's expense.

In concordance with the NCI Genomic Data Sharing Policy, genomic data generated in this study will be deposited in dbGaP and will be available in a controlled-access manner.

#### 11. **REPORTING ADVERSE EVENTS**

DEFINITION: AE means any untoward medical occurrence associated with the use of a drug in humans, whether or not considered drug related. An AE can therefore be any unfavorable and unintended sign), symptom, or disease temporally associated with participation in a study, whether or not related to that participation. This includes all deaths that occur while a participant is on a study.

Please note that all abnormal clinical laboratory values that are determined to be of clinical significance based on a physician's assessment are to be reported as AEs. Those labs determined to be of no clinical significance or of unknown clinical significance (per the physician's assessment) should not be reported as AEs. Any lab value of unknown clinical significance should continue to be investigated/followed-up further for a final determination, if possible.

A list of AEs that have occurred or might occur can be found in §6.2 Reported Adverse Events and Potential Risks, as well as the Investigator Brochure or package insert.

# 11.1 Adverse Events

# 11.1.1 Reportable AEs

All AEs that occur after the informed consent is signed and baseline assessments are completed (including run-in) must be recorded on the AE CRF (paper and/or electronic) whether or not related to study agent.

# 11.1.2 AE Data Elements:

The following data elements are required for AE reporting.

- AE verbatim term
- NCI Common Terminology Criteria for Adverse Events version 4.0 (CTCAE v4.0) AE term (MedDRA lowest level term)
- CTCAE (MedDRA) System Organ Class (SOC)
- Event onset date and event ended date
- Treatment assignment code (TAC) at time of AE onset
- Severity grade
- Attribution to study agent (relatedness)
- Whether or not the event was reported as a SAE
- Whether or not the subject dropped due to the event
- Outcome of the event

# 11.1.3 Severity of AEs

11.1.3.1 Identify the AE using the CTCAE version 4.0. The CTCAE provides descriptive terminology (MedDRA lowest level term) and a grading scale for each AE listed. A copy of the CTCAE can be found at http://ctep.cancer.gov/protocolDevelopment/electronic\_applications/ctc.htm

AEs (except female genital AEs) will be assessed according to the grade associated with the CTCAE term. Female genital AEs will be assessed according to the NIAID DAIDS Female Genital Grading Table (FGGT) (weblinks below; Appendix B), rather than using CTCAE:

http://www.mtnstopshiv.org/sites/default/files/attachments/Addendum 1 Female Genital Grading Table v1 Nov 2007. pdf or https://rsc.tech-res.com/docs/default-source/safety/addendum 1 female genital grading table v1 nov 2007.pdf

If an AE can be found in both CTCAE and FGGT, FGGT will be used for the assessment.

Other AEs that do not have a corresponding CTCAE term will be assessed according to the general guidelines for grading used in the CTCAE v4.0. as stated below.

# CTCAE v4.0 general severity guidelines:

Grade	Severity	Description
1	Mild	Mild; asymptomatic or mild symptoms; clinical or diagnostic observations only; intervention not indicated.
2	Moderate	Moderate; minimal, local or noninvasive intervention indicated; limiting age-appropriate instrumental activities of daily living (ADL)*.
3	Severe	Severe or medically significant but not immediately life-threatening; hospitalization or prolongation of hospitalization indicated; disabling; limiting self- care ADL**.
4	Life-threatening	Life-threatening consequences; urgent intervention indicated.

Grade	Severity	Description
5	Fatal	Death related to AE.

#### ADL

\*Instrumental ADL refers to preparing meals, shopping for groceries or clothes, using the telephone, managing money, *etc.* 

\*\*Self-care ADL refers to bathing, dressing and undressing, feeding self, using the toilet, taking medications, and not bedridden.

#### 11.1.4 Assessment of relationship of AE to treatment

The possibility that the AE is related to study agent will be classified as one of the following: not related, unlikely, possible, probable, definite.

#### 11.1.5 Follow-up of AEs

All AEs, including lab abnormalities that in the opinion of the investigator are clinically significant, will be followed according to good medical practices and documented as such.

#### 11.2 Serious Adverse Events

11.2.1 DEFINITION: Regulations at 21 CFR §312.32 (revised April 1, 2014) defines an SAE as any untoward medical occurrence that at any dose has one or more of the following outcomes:

- Death
- A life-threatening AE
- Inpatient hospitalization or prolongation of existing hospitalization
- A persistent or significant incapacity or substantial disruption of the ability to perform normal life functions
- A congenital anomaly or birth defect
- Important medical events that may not be immediately life-threatening or result in death or hospitalization should also be considered serious when, based upon appropriate medical judgment, they may jeopardize the participant and may require intervention to prevent one of the other outcomes.

#### 11.2.2 Reporting SAEs to DCP

11.2.2.1 The Lead Organization and all Participating Organizations will report SAEs on the DCP SAE Report Form found at http://prevention.cancer.gov/clinical-trials/clinical-trials-management/protocol-information-office/pio-instructions-and-tools/2012-consortia.

11.2.2.2 Contact the DCP Medical Monitor by phone within 24 hours of knowledge of the event.

DCP Medical Monitor: [name], PhD Breast and Gynecologic Cancer Research Group Division of Cancer Prevention [name][name] 20892-9783 [contact] Email: [contact] Include the following information when calling the Medical Monitor:

- Date and time of the SAE
- Date and time of the SAE report
- Name of reporter
- Call back phone number
- Affiliation/Institution conducting the study
- DCP protocol number
- Title of protocol
- Description of the SAE, including attribution to drug

11.2.2.3 The Lead Organization and all Participating Organizations will email written SAE reports to DCP's Regulatory Contractor CCS Associates, Inc. (CCSA; [contact]) at [contact] within 48 hours of learning of the event using the fillable PDF SAE Report Form.

11.2.2.4 The DCP Medical Monitor and CCSA regulatory and safety staff will determine which SAEs require FDA submission as IND safety reports.

11.2.2.5 The Lead Organization and all Participating Organizations will comply with applicable regulatory requirements related to reporting SAEs to the IRB/IEC.

#### 11.2.3 Follow-up of SAE

Site staff should send follow-up reports as requested when additional information is available. Additional information should be entered on the DCP SAE Report Form in the appropriate format. Follow-up information should be sent to DCP as soon as available. SAE related to the study agent will be followed until resolved, or deemed unlikely to further resolved by the Protocol Chair, or until the subject withdraws consent for further follow-up. SAE unrelated or unlikely to be related to study agent will be followed for at least 30 days after the last dose of study agent.

#### **12.** STUDY MONITORING

#### 12.1 Data Management

This study will report clinical data using the OnCore application from Forte Research Systems, Inc., as stated in the Master Data Management Plan. All users of the database will have appropriate education, training and experience to perform assigned tasks. The data collection and management will be done according to the Consortia 2012 DMP.

#### 12.2 Case Report Forms

Participant data will be collected using protocol-specific case report forms (CRF) developed from the standard set of DCP Chemoprevention CRF Templates and utilizing NCI-approved Common Data Elements (CDE). The approved CRFs will be used to create the electronic CRF (e-CRF) screens in the OnCore application. Consortia site staff will enter data into the e-CRF for transmission to DCP according to pre-established DCP standards and procedures. Amended CRF will be submitted to the DCP Protocol Information Office for review and approval. Approved changes will be programmed into the OnCore database by the Consortium Data Management staff.

CRF Submission Information: University of Arizona Early Phase Chemoprevention Consortium Office Attn: [name] [name] [contact] [contact]

#### **12.3** Source Documents

Source documentation for this trial will consist of protocol-specific source documents as well as clinical and research laboratory reports. In the event of a Serious Adverse Event, medical records related to the event will be sought for source documentation of the event and its treatment, if any.

#### 12.4 Data and Safety Monitoring Plan

The University of Arizona Cancer Center (UACC) Data and Safety Monitoring Board (DSMB) will provide oversight for subject safety for all UA Consortium clinical trials consistent with the National Institutes of Health Policy for Data and Safety Monitoring dated June 10, 1998; further guidance statement issued by the NIH on June 5, 2000, and the policy for Data and Safety Monitoring by Data and Safety Monitoring Boards. The UACC DSMB meets quarterly.

Regular monthly meetings of the UA Consortium, are used as a forum to review accrual rates, problematic issues relating to accrual and protocol implementation, adverse events occurrence, follow-up, and reporting; submission of all required study reports; and progress and outcomes of laboratory analyses.

#### 12.5 Sponsor or FDA Monitoring

The NCI, DCP (or their designee), pharmaceutical collaborator (or their designee), or FDA may monitor/audit various aspects of the study. These monitors will be given access to facilities, databases, supplies and records to review and verify data pertinent to the study.

#### 12.6 Record Retention

Clinical records for all participants, including CRFs, all source documentation (containing evidence to study eligibility, history and physical findings, laboratory data, results of consultations, *etc.*), as well as IRB records and other regulatory documentation will be retained by the Investigator in a secure storage facility in compliance with Health Insurance Portability and Accountability Act (HIPAA), Office of Human Research Protections (OHRP), Food and Drug Administration (FDA) regulations and guidances, and NCI/DCP requirements, unless the standard at the site is more stringent. The records for all studies performed under an IND will be maintained, at a minimum, for two years after the approval of a New Drug Application (NDA). For NCI/DCP, records will be retained for at least three years after the completion of the research. NCI will be notified prior to the planned destruction of any materials. The records should be accessible for inspection and copying by authorized persons of the Food and Drug Administration. If the study is done outside of the United States, applicable regulatory requirements for the specific country participating in the study also apply.

#### 12.7 Cooperative Research and Development Agreement (CRADA)/Clinical Trials Agreement (CTA)

Not applicable.

#### **13. STATISTICAL CONSIDERATIONS**

#### 13.1 Study Design/Description

This is a pilot study aiming to assess the feasibility of a combination regimen of 5-FU and imiquimod. As mentioned in Section 3, the study will have two phases:

1. Initiation phase, which will include a total of 12 to 14 participants

2. Extension phase, which will include no more than the original 12 to 14 participants. Study participants will be given the option to continue treatment during the extension phase. Data collected during this phase will be used to further assess the safety, tolerability, and efficacy of the combination therapy.

# 13.2 Randomization/Stratification

No randomization/stratification will be performed.

# 13.3 Accrual and Feasibility

We plan to screen/consent 14 women, assuming a screen fail rate of 10%, to have at least 12 initiating agent intervention. The projected accrual rate is 4/month and it is anticipated that the accrual will take 3-4 months. In addition, it is expected that additional delays and deferrals would occur due to menstrual periods and/or other medically-indicated reasons.

# 13.4 Primary Objective, Endpoint(s), Analysis Plan

The primary objective of the study is to assess the feasibility of intravaginal use 5-FU and imiquimod on alternating weeks in women with biopsy confirmed high grade cervical squamous intraepithelial lesions (i.e., CIN3 lesions and CIN2 lesions diagnosis confirmed by positive p16 immunohistochemistry staining).

Feasiblity is evaluated based on safety and tolerability of the study intervention. For safety, we will assess the number of participants experiencing the dose limiting toxicity (DLT). DLT is defined as Grade 2 or greater toxicity (or Grade 1 toxicity of any genital lesion (blisters, ulcerations, or pustules)) that is possibly, probably, or definitely related and lasts for more than 5 days. For tolerability, we will assess the number of participants who are not able to apply at least 50% of the treatment due to DLT.

The proportion of participants experiencing DLT and the proportion of tolerable participants will be reported along with their 95% confidence intervals. We plan to accrue at least 12 participants to evaluate the feasibility of the intervention to determine whether this intervention is worth exploring further in a subsequent trial. If  $\geq 33\%$  experience DLT, we will not proceed with further exploration using the combined agent intervention.

In the prior trial conducted by [name], self-administration of 5FU once every two weeks for a total of 16 weeks did not result in adverse events that were Grade 2 or higher. Addition of imiquimod in alternating weeks to the 5FU alone treatment may increase the type or severity of the adverse events than those observed with 5FU alone. Nevertheless, our proposed intervention is expected to have an improved safety profile than prior trials of intravaginal imiquimod because of the less frequent dosing of imiquimod employed in our trial. Therefore, we do not expect to observe a toxicity rate of greater than 30% with our study intervention.

The probabilities of observing DLT in 33% or more participants for toxicity rates no greater than 30% are listed below:

 	
Projected toxicity rate	Probability of observing DLT in
	≥ 33% participants
≤ 5%	< 1%
10%	2.6%
20%	20.5%
30%	50.7%

The probabilities of having less than 66% tolerable participants with projected tolerability rates of 50-80% are listed below:

Projected tolerability rate	Probability of < 66% tolerable participants
80%	7.3%

70%	27.6%
60%	56.2%
50%	80.6%

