#### 1. **OBJECTIVES**

#### 1.1 **Primary Objectives**

Assess feasibility, evaluated based on safety and tolerability, of a combination agent intervention (once-weekly self-administered intravaginal application of 5-fluorouracil alternating with once-weekly provider-applied imiquimod) for treatment of high-grade cervical squamous intraepithelial lesions

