# 8. CRITERIA FOR EVALUATION AND ENDPOINT DEFINITION

# 8.1 Primary Endpoint

The primary endpoint is feasibility of a combination agent intervention (once-weekly self-administered intravaginal 5-FU alternating with once-weekly provider-administered imiquimod) in women with biopsy confirmed high grade cervical squamous intraepithelial lesions (i.e., CIN3 lesions and CIN2 lesions diagnosis confirmed by positive p16 immunohistochemistry staining).

Feasiblity is evaluated based on safety and tolerability of the study intervention. For safety, we will assess the number of participants experiencing the dose limiting toxicity (DLT). DLT is defined as Grade 2 or greater toxicity (or Grade 1 toxicity of any genital lesion (blisters, ulcerations, or pustules)) that is possibly, probably, or definitely related and lasts for more than 5 days. For tolerability, we will assess the number of participants who are not able to apply at least 50% of the treatment due to DLT.

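### Tolerability counts only women who already have a DLT, so it adds nothing to the go/no-go decision and misses women who receive less than half the treatment because of other related events

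*Combined protocol and SAP*

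**What the plan says.** The primary objective in Section 1.1 is to "Assess feasibility, evaluated based on safety and tolerability, of a combination agent intervention". Sections 8.1 and 13.4 give the two components the same definitions.

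- **Safety** is the number of women with a DLT. On severity, "DLT is defined as Grade 2 or greater toxicity (or Grade 1 toxicity of any genital lesion (blisters, ulcerations, or pustules" and so on; the toxicity must also be one "that is possibly, probably, or definitely related and lasts for more than 5 days".
- **Tolerability**, in Section 13.4: "For tolerability, we will assess the number of participants who are not able to apply at least 50% of the treatment due to DLT". Section 8.1 has the same definition.

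Both proportions are to be reported with 95% confidence intervals. The sample size is stated as "We plan to accrue at least 12 participants to evaluate the feasibility of the intervention". One decision rule is given: if 33% or more "experience DLT, we will not proceed with further exploration using the combined agent intervention".

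For tolerability there is only a table, introduced by "The probabilities of having less than 66% tolerable participants with projected tolerability rates of 50-80% are listed below". No action is attached to the 66%. The same section does not expect a toxicity rate above 30%.

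Three other places bear on the point:

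- Section 5.6 ends dosing after a related Grade 3 or 4 event and sets no minimum duration.
- Section 8.3 allows a woman to come off agent for any adverse event.
- Appendix B grades vulvar or vaginal itching as Grade 1 even when it interferes moderately with usual activities.

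**The concern.** Two components of a primary endpoint should be able to disagree. A regimen may cause few DLTs and still be one that women do not keep applying. Here tolerability is conditional on a DLT, so the second component can only repeat part of the first.

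Two things follow. First, the tolerability result cannot alter the decision on whether to study the combination further. Second, a woman who receives less than half of her applications because of a related event that is too short, or too low in grade, is counted as having tolerated the treatment. The reported tolerable proportion could then look better than the women's actual experience, and a reader of the results would not see the difference.

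**Working it through.** **Inputs.** n = 12 to 14 (Sections 3 and 13.1; at least 12 in 13.4); DLT no-go at 33% or more; tabulated tolerability figure of less than 66%; expected toxicity of no more than 30% (all Section 13.4). Both endpoints are reported on the intent-to-treat population (Section 13.6), so they share a denominator.

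**Step 1. Reproduce the plan's tables** (exact binomial, n = 12).

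- P(4 or more DLTs) at true rates of 5, 10, 20 and 30% is 0.2%, 2.6%, 20.5% and 50.7%. The plan gives <1%, 2.6%, 20.5% and 50.7%.
- P(7 or fewer tolerable) at true rates of 80, 70, 60 and 50% is 7.3%, 27.6%, 56.2% and 80.6%. The plan gives the same.

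Both tables are correct as binomial calculations.

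**Step 2. Nesting.** Let d be the number with a DLT and i the number non-tolerable. By definition i ≤ d, so the tolerable proportion is 1 − i/n ≥ 1 − d/n. If it is below 0.66, then d/n ≥ i/n > 0.34, which is already above 0.33. Whole-number cut-offs:

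| n | Fewest DLTs meeting the no-go | Fewest non-tolerable giving <66% tolerable | DLT proportion then at least |
|---|---|---|---|
| 12 | 4 (33.3%) | 5 (7/12 = 58.3% tolerable) | 5/12 = 41.7% |
| 13 | 5 (38.5%) | 5 (8/13 = 61.5% tolerable) | 5/13 = 38.5% |
| 14 | 5 (35.7%) | 5 (9/14 = 64.3% tolerable) | 5/14 = 35.7% |

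Enumerating every pair (d, i) for n = 10 to 14 finds none in which tolerability is below 66% and the DLT rule passes. That probability is exactly 0.

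**Step 3. How often the figure would be crossed at all.** At a true DLT rate of 30% and n = 12, the DLT no-go is met with probability 50.7%. Fewer than 66% are tolerable with probability 2.4% if half the women with a DLT fall below half the treatment, and 27.6% if all do.

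**Step 4. The table rows.** A tolerability rate t requires a DLT rate of at least 1 − t:

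- 80% needs at least 20%, and 70% needs at least 30%
- 60% needs at least 40%, and 50% needs at least 50%

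The DLT table stops at 30%, which is also the stated expectation. The last two tolerability rows lie outside it unless tolerability means something wider than the written definition.

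**Step 5. Who is scored tolerable.** Take a woman who receives fewer than 4 of 8 applications.

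- A related Grade 3 event lasting 4 days ends her dosing under Section 5.6. It is not a DLT, because it did not last more than 5 days. She is scored tolerable.
- She gives up because of Grade 1 itching with moderate interference. Without a genital lesion, Grade 1 is not a DLT at any duration. She is scored tolerable.

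**Step 6. Illustration only.** If 6 of 12 women fell below half for related non-DLT events and none had a DLT, the plan would report tolerability of 12/12 (exact 95% interval 73.5% to 100%). A broader count would give 6/12 (21.1% to 78.9%).

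Under assumed rates (half of the women with a DLT fall below half the treatment, as do 10% to 30% of those without one), a broader count would be below 66% while the DLT rule passes with these probabilities:

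- 1.5% to 31.9% at a DLT rate of 10%
- 2.2% to 28.7% at 20%
- 1.7% to 18.8% at 30%

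Under the written definition each of these is 0.

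**The case against.** A subset can still be informative. The planned proportion can be estimated (10/12 gives an exact interval of 51.6% to 97.9%), and it distinguishes DLTs managed by delay or omission from those that cost half the treatment. A reader might infer that half the primary objective cannot be answered. The documents do not support that: what goes unanswered is intolerance that is not due to a DLT.

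A reader might also infer that a stated tolerability test can never fail. Section 13.4 states no such test; 66% appears only in the table. This objection stands, and it means that tolerability has no stated role in the decision.

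The DLT threshold is low. It includes Grade 1 genital lesions, and under Appendix B Grade 2 covers pain needing non-narcotic medication and discharge needing a pad. Much troublesome toxicity will therefore qualify if it lasts long enough. That narrows the gap to shorter events and to Grade 1 events without lesions, but does not close it.

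It is tempting to go further and say that many women will probably give up because of low-grade effects. The documents do not show this. The 48% with side effects on 5-FU (Section 2.2) and the more than 90% on imiquimod are rates of side effects, not of stopping. On 5-FU, no woman reported interference with usual activities and 86% were satisfied. The imiquimod figure comes from a 42-dose regimen, against at most 8 doses here, and another cited imiquimod trial had no discontinuations for side effects (Section 6.2).

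Non-DLT problems are partly visible through the adverse event summaries (Section 13.7) and the optional survey, but neither is a tolerability endpoint. Tabulating pessimistic rates is not an error, since an expectation is not a bound; the remaining fault is that the two tables cover different ranges of DLT rate without saying so.

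**Conclusion.** The point holds in this form. As defined, tolerability is contained in the DLT count, and the 66% figure cannot be crossed unless the DLT no-go is already met, so it adds nothing to the go/no-go decision. This follows from the definitions and a shared denominator, and needs no assumption about event rates. Women who receive less than half the treatment because of related events outside the DLT definition are scored tolerable; for Grade 3 or 4 events of 5 days or less this arises directly from Sections 5.6 and 8.1 read together. The 60% and 50% table rows imply DLT rates of at least 40% and 50%, against an expectation of no more than 30%.

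How many women would be misclassified cannot be derived from the documents. The 6-of-12 case and the assumed rates show what could happen and are not a forecast.

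**What to change.** 1. In Sections 8.1 and 13.4, keep the DLT-based count. Beside it, report with an exact 95% interval the proportion who applied less than half of their assigned applications because of any related adverse event or side effect, DLT or not, and list the reasons. Say whether half refers to 8 or 16 applications for women who enter the extension.
2. State which definition the tolerability table refers to, and whether 66% is a decision threshold. Without a threshold, the added count makes the problem visible but does not affect the decision.
3. Reconcile Sections 5.6 and 8.1 on how a related Grade 3 or 4 event of 5 days or less that ends dosing is counted.

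**Cost.** No new assessments are needed. Application counts come from the calendar and provider records (Section 5.7); attribution, onset and end dates, and the flag for dropping out because of an event are adverse event data elements (Section 11.1.2). The calendar is described as recording when a dose was applied, not why one was missed, so reasons for single omissions may have to be matched from event dates. The broader tolerable proportion can only be equal to or lower than the planned one. The text is at Amendment 11 and provides for women who had already completed participation before the survey was offered, so outcomes may have been seen. If so, label the count as added by amendment; this is one reason to add it rather than replace the primary definition.
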